4.5. Analysis Populations

4.5.1. Safety Population

The Safety Population includes all subjects who receive any amount of study drug (PB2452 or matching placebo). The Safety Population will be analyzed for all safety assessments. Subjects in the Safety Population will be analyzed as treated.

4.5.2. Pharmacokinetic (PK) Population

The PK population includes subjects in the safety population who have ≥ 1 measurable PK concentration. The PK population will be used to summarize all PB2452 blood concentrations. Subjects in the PK population will be analyzed as treated.

4.5.3. Modified Intention-to-Treat (mITT) Population

Modified Intention-to-Treat (mITT) population includes all subjects randomly assigned to study treatment, who take any amount of study drug (PB2452 or placebo). Subjects will be analyzed according to the treatment they are randomized to.

5. Subject Disposition

5.1. Disposition

Subject disposition will be presented by Part for all screened subjects, including number of screen-failed subjects, number of subjects enrolled (i.e. receiving ticagrelor) and number of subjects randomized.

Number and percentage of subjects in the following categories will be summarized as appropriate:

- Screen failed

- Enrolled
- Enrolled, but Not Randomized
- Randomized
- mITT Population
- Safety Population
- Per-Protocol Population
- PK Population

Additionally, a summary of study completion and treatment completion status will be presented along with reasons for discontinuation if any.

All tables and listings will be done for both Part A and Part B of the study, separately.

5.2. Protocol Deviations and Eligibility Criteria Deviations

Protocol deviations will be presented by Part in a data listing. Eligibility with regards to inclusion and exclusion criteria will be listed in a separate listing.

6. Demographics and Baseline Characteristics

6.1. Demographics

Demographic information collected at screening will be presented by Part in a data listing for both Part A and Part B. Descriptive statistics will be calculated for the following continuous demographic characteristics: age (years, calculated as the integer part of [date of informed consent - date of birth]/365.25), weight (kg), height (cm), and body mass index (BMI, kg/m²). Frequency counts will be tabulated for the categorical variables of sex, race, ethnicity and renal function (Normal [GFR \geq 90], Mild [GFR 60-89], Moderate [GFR 30-59], Severe [GFR \leq 29]). The summaries will be presented by treatment groups and overall for the safety population.

All tables and listings for Demographics and Baseline Characteristics will be done for both Part A and Part B of the study, separately.

6.2. Medical History

All tables and listings for Medical History will be done by Part for both Part A and Part B of the study.

The medical history data will be coded using the Medical Dictionary for Regulatory Activities (MedDRA; version 21.0 or higher) and presented in a data listing.

7. Treatments and Medications

All tables and listings for Treatments and Medications will be done for both Part A and Part B of the study.

7.1. Prior and Concomitant Medications

Prior medications are defined as medications taken prior to the initiation of study drug. Concomitant medications are defined as medications that were taken on or after the initiation of study drug. A medication can be considered as both prior and concomitant if the medication is taken prior to the initiation of study drug and continued into the treatment period. Ticagrelor and aspirin, which will be received by all study subjects, are considered pre-treatments. Medications taken prior to ticagrelor, concomitant with ticagrelor and concomitant with the study treatments PB2452 and placebo will be presented separately.

Prior and concomitant medications will be coded using the latest version of the World Health Organization Drug Dictionary (version March 2019 or later) and presented in a listing.

All tables and listings for prior and concomitant medications will be done for both Part A and Part B of the study.

7.2. Medical and Surgical Procedures

Medical and surgical procedures will be presented in a listing, by Part.

7.3. Study Treatments

Study drug (PB2452 or matching placebo), aspirin, and ticagrelor administration will be presented in data listings, by Part.

8. Safety Analysis

All tables and listings for Safety Analysis will be done for both Part A and Part B of the study, separately.

Safety will be assessed by examination of adverse events, physical examination findings, vital signs, clinical laboratory measurements, antibodies to study drug and 12 lead ECGs. These results will be presented for the Safety Population by Part.

8.1. Adverse Events

An AE is defined as any untoward medical occurrence associated with the use of a drug in humans, whether or not it is considered drug-related.

A TEAE is defined as any AE not present before exposure to study drug or any AE already present that worsens in intensity or frequency after exposure to study drug.

All AEs will be coded using MedDRA (version 21.0 or higher) by system organ class (SOC) and preferred term (PT).

All summary tables, except from the overall summary table and summary by relationship to ticagrelor, will be based on TEAEs. Frequency and percentage at subject level as well as number of events will be presented in the summaries. The SOCs will be displayed in descending order of overall frequency and then alphabetically. The PTs will be displayed in descending order of overall frequency and then alphabetically within SOC. A subject with 2 or more AEs within the same level of summarization will be counted only once in that level using the most severe (for the severity table) or most related (for the relationship to study drug table) incident.

Summary tables will be presented by Part and by treatment group. Percentages will be based upon the number of subjects in the safety population overall (for the corresponding Part) and within each treatment group.

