### **3.2 SELECTION OF STUDY POPULATION**

Male or female subjects will be evaluated in up to 5 cohorts in the US, North America. To ensure the study clinic has sufficient subjects available for dosing for any cohort, additional subjects may be asked to present to the clinic for check in. The number of subjects brought in for check-in and pre-dosed with ticagrelor will be at the discretion of the study clinic personnel/ principal investigator to ensure there is a sufficient number of subjects available for dosing with study drug for a given cohort. Subjects who check in to the clinic may be dosed with ticagrelor in preparation for dosing with the study drug according to the Schedule of Events (Appendix 7.1). Extra subjects may be dosed with ticagrelor, so on the day of randomization there is a sufficient number of subjects available to fill the cohort.

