3.3. Treatments

Study Drug will refer to PB2452 or matching placebo.

PART A:

PB2452: PB2452 IV infusion, prepared according to the Pharmacy Manual, was administered on Day 1 for up to 48 hours. The total dose for each subject was 18g. The infusion rate was not to

exceed 18g over 30 minutes and the concentration was not to exceed 24g in 250mL. Subjects were not to receive more than 250 mL of study drug infusion within any 1-hour period. Two cohorts were enrolled in Part A, both at a total dose of 18g.

For each cohort, the dose, infusion rate, and duration was communicated from the Sponsor to the study site, PPD, in a Dosing Memo issued prior to initiation of each treatment cohort.

Matching Placebo: 0.9% sodium chloride single IV infusion, administered on Day 1, was delivered at a rate and volume matching the active infusion.

Ticagrelor: Ticagrelor 90 mg oral tablet (immediate release) administered as 180 mg (2 × 90 mg tablets) loading dose plus 90 mg every 12 hours for 4 additional doses.

ASA: During Screening, starting on Study Day -7, subjects received ASA (enteric coated) 81 mg QD to be taken through to the morning of Day 1, prior to receiving study medication. Subjects who were already taking ASA daily before entering the study must have been willing to document self-administered daily 81 mg dose of ASA between Day -7 and -3, accept ASA 81 mg administered at the clinical site between Day -2 and Day 1, and suspend further ASA doses until discharge from the clinical facility.

PART B:

PB2452: PB2452 IV infusion, prepared according to the Pharmacy Manual, was administered on Day 1 for up to 48 hours. For each cohort, the dose, infusion rate, and duration was communicated from the Sponsor to the study site, PPD, in a Dosing Memo issued prior to initiation of each treatment cohort. One cohort in Part B was enrolled, at a total dose of 36 g.

Matching Placebo: 0.9% sodium chloride single IV infusion, was delivered at a rate and volume matching the active infusion.

Ticagrelor: Ticagrelor 90 mg oral tablets (immediate release) was administered as a 180 mg (2 × 90 mg tablets) oral dose every 12 hours for 5 total doses.

4. General Statistical Considerations

All statistical analyses will be conducted using statistical analysis system SAS® Version 9.4 or higher (SAS Institute, Cary, NC). For tables and data listings with no data, titles and footnotes will be presented, and “No data to display” will be presented.

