8.1.2. Relationship of Adverse Events

The relationship of AE to study drug and ticagrelor will be classified by the Investigator as unrelated, possible, probable, and definite. Treatment-emergent AEs will be summarized by SOC, PT, and relationship to study drug; AEs will be summarized by SOC, PT, and relationship to ticagrelor. A subject with 2 or more TEAEs within the same level of summarization will be counted only once in that level using the most related incident.

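### The summary of adverse events by relationship to ticagrelor leaves out subjects who took ticagrelor but received no study drug, so it does not give the rate among those exposed

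*SAP*

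**What the plan says.** Four statements in the SAP fix who is counted.

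- Section 3.3: "Study Drug will refer to PB2452 or matching placebo". Ticagrelor is pretreatment, not study drug.
- Section 4.5.1: "The Safety Population includes all subjects who receive any amount of study drug (PB2452 or matching placebo").
- Opening of section 8, on safety results generally: "These results will be presented for the Safety Population by Part".
- Section 8.1, on AE tables: "Percentages will be based upon the number of subjects in the safety population overall (for the corresponding Part) and within each treatment group".

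Two statements concern the ticagrelor table itself. Section 8.1.2 plans it: "AEs will be summarized by SOC, PT, and relationship to ticagrelor". Section 8.1 sets the events it covers: "All summary tables, except from the overall summary table and summary by relationship to ticagrelor, will be based on TEAEs". Neither names a different population.

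The documents also foresee subjects who take ticagrelor and go no further. Section 3.2 of both protocol parts says "Extra subjects may be dosed with ticagrelor" so that the cohort can be filled on the day of randomization. SAP section 5.1 reports the "number of subjects enrolled (i.e. receiving ticagrelor") separately from the number randomized, and has a disposition line for those enrolled but not randomized. That set is used for disposition only.

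**The concern.** The event scope and the population of this table do not match. Lifting the restriction to treatment-emergent events lets in events from before the infusion, when ticagrelor is the drug being given (with aspirin in Part A). But a subject is counted only if he or she went on to receive PB2452 or placebo.

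Some departures before the infusion can be caused by the outcome being tabulated. In both parts ticagrelor starts on Day -2, eligibility is checked again on Day -1, and only subjects who still meet the criteria are randomized on Day 1 (protocol sections 3.1 and 3.5). Exclusion criterion 7 includes active bleeding and hypersensitivity or allergy to ticagrelor, and section 3.3.1 allows withdrawal for a serious or intolerable AE. A subject who bleeds or reacts during pretreatment can therefore leave the table because of that event.

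At stake is what the percentage means. A table headed by relationship to ticagrelor will be read as describing people exposed to ticagrelor. It describes only those who also received study drug.

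**Working it through.** The documents give no AE rate, no count of surplus subjects and no power calculation on this point, so there is no stated figure to reproduce. The check compares the definitions and then illustrates the size under stated assumptions.

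**1. Definitions.** Enrolled means received ticagrelor (SAP 5.1). Safety Population means received PB2452 or placebo (SAP 4.5.1). The difference is everyone given ticagrelor but no study drug: surplus subjects, subjects withdrawn or found ineligible between Day -2 and Day 1, and anyone randomized but never infused. AEs are assessed from consent (protocol 3.5.2.2), and the eCRF has its own line for relationship to ticagrelor (protocol 3.5.2.1). The data for this group are therefore collected, but the summary does not use them.

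**2. Notation.** S = Safety Population size; E = exposed to ticagrelor, no study drug; x and y = subjects with a ticagrelor-related AE in S and in E.

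- Rate in the SAP table: x/S
- Rate among all exposed: (x + y)/(S + E)
- Share of exposed subjects omitted: E/(S + E)

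The exposed rate is a weighted average of x/S and y/E. The table therefore understates it when y/E > x/S, overstates it when y/E < x/S, and agrees when the two are equal.

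**3. Inputs.** Cohorts of about 8 to 12 (SAP 3.1); two cohorts enrolled in Part A and one in Part B (SAP 3.3). So S is about 16 to 24 in Part A and 8 to 12 in Part B. E is not given; I assume 1, 2 or 4 per cohort.

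**4. Share omitted.** Part A is shown; Part B halves S and E and gives the same percentages.

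| S | E = 2 | E = 4 | E = 8 |
|---|---|---|---|
| 16 | 2/18 = 11.1% | 4/20 = 20.0% | 8/24 = 33.3% |
| 24 | 2/26 = 7.7% | 4/28 = 14.3% | 8/32 = 25.0% |

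**5. A single event, outside the Safety Population** (x = 0, y = 1). The SAP table shows 0%. The exposed rate runs from 1/32 = 3.1% to 1/18 = 5.6% in Part A, and from 1/16 = 6.25% to 1/9 = 11.1% in Part B.

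**6. Direction.** Part A with S = 16, E = 4, x = 2; the SAP table shows 2/16 = 12.5% throughout.

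| y | Rate among all exposed | SAP table is |
|---|---|---|
| 0 | 2/20 = 10.0% | too high |
| 1 | 3/20 = 15.0% | too low |
| 2 | 4/20 = 20.0% | too low |

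With E = 8 and y = 1 the two agree: 3/24 = 12.5%, because 1/8 = 2/16.

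**The case against.** The best defence is that the Safety Population suits the trial's question. The primary safety objective compares PB2452 with placebo after ticagrelor pretreatment, and no objective asks for an AE rate on ticagrelor. The AE tables are laid out by treatment group, and a subject who was never randomized has none. This stands for the treatment-emergent tables, which should not change. It is weaker for a table whose subject is ticagrelor and whose event scope is not tied to study drug.

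The second defence is that nothing is hidden. All AEs are listed (SAP 8.1.1), serious AEs and AEs leading to early discontinuation have their own listings by Part (8.1.6, 8.1.7), and ticagrelor administration is listed (7.3). Protocol section 3.6.3 keeps data from subjects outside an analysis population in the listings while leaving them out of summary statistics. With cohorts this small, a reader can go through a listing subject by subject. This also stands. A reader might infer that AEs in these subjects go unreported; they do not. Only the summary percentage omits them.

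It could also be argued that the All Subjects column in SAP section 4 already covers the group. It does not: section 8 ties safety results, and section 8.1 ties AE percentages, to the Safety Population, and no column is defined for subjects without study drug.

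**Conclusion.** The point holds as a minor one. By definition, the ticagrelor-relationship table excludes ticagrelor-exposed subjects who received no study drug, so it does not estimate the rate among the exposed. How many are omitted is unknown; about 8% to 33% follows only from the assumed 1 to 4 per cohort of 8 to 12.

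Three stronger readings are tempting and are not supported.

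- *The rate is understated by design.* That requires AEs to be what keeps subjects from being randomized. This is possible, but nowhere said to be expected. The only stated reason for extra pre-dosing is to fill the cohort, and surplus subjects who leave without an AE make the table's rate too high.
- *The table distorts dose-limiting-toxicity decisions*, because attributing an event to ticagrelor removes it from that count. The Safety Review Committee judges individual events in subjects known to have had PB2452 (protocol 3.4.2.3; SAP 8.1.4), meets between cohorts (protocol 3.4.2.1), and passes its findings to the analysis in a spreadsheet. The SAP covers the final analysis and describes enrollment as finished. No passage makes this table an input to those decisions.
- *The SAP widened the events in order to capture pretreatment.* That is the effect, but the SAP gives no reason for the exemption.

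**What to change.** For the summary by relationship to ticagrelor only:

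1. Define in SAP section 4.5 an analysis set of all subjects who received ticagrelor, by Part. Enrolled is at present a disposition count, not an analysis population, so the definition has to be added.
2. Use that set as the denominator for the overall percentage, and add a column *ticagrelor-exposed, no study drug*. That label also covers anyone randomized but not infused.
3. Keep the Safety Population and the treatment-group columns for all treatment-emergent AE tables.

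The cost is one population definition and one extra column. No new data are needed, since AEs are assessed from consent and relationship to ticagrelor is already on the eCRF.

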8.1.1. Incidence of Adverse Events

All AE tables and listings will be provided by Study Part.

All AEs will be presented in a data listing, and all TEAEs will be presented in a summary table by SOC, PT, treatment group and overall. Additional table of TEAEs will be presented in a summary by PT only.

An overall summary table, will be created with following categories:

- Any TEAE
- Any study-drug-related TEAE
- Any severe TEAE
- Any severe study-drug-related TEAE
- Any serious adverse event (SAE)
- Any treatment-emergent, study-drug-related SAE
- Any AE leading to early study discontinuation
- Any DLT
- Any Infusion Site Reactions (ISR)
- Any death

The definition of DLT is defined in Section 8.1.4. For the purpose of above summary, a study-drug-related AE is an AE with definite, probable, possible, or missing relationship to the study drug on eCRF. Study drug refers to PB2452 or matching placebo.

8.1.2. Relationship of Adverse Events

The relationship of AE to study drug and ticagrelor will be classified by the Investigator as unrelated, possible, probable, and definite. Treatment-emergent AEs will be summarized by SOC, PT, and relationship to study drug; AEs will be summarized by SOC, PT, and relationship to ticagrelor. A subject with 2 or more TEAEs within the same level of summarization will be counted only once in that level using the most related incident.

8.1.3. Severity of Adverse Event

The severity (or intensity) of an AE refers to the extent to which it affects the subject's daily activities and will be classified as mild, moderate, or severe. The TEAEs will be summarized by SOC, PT, severity (including category 'Missing' for events with missing severity assessment on eCRF) and treatment group. A subject with 2 or more TEAEs within the same level of summarization will be counted only once using the most severe event.

8.1.4. Dose Limiting Toxicities

The SRC will review all AEs and all laboratory and ECG Holter monitoring abnormalities according to Common Terminology Criteria for Adverse Events (CTCAE) v5 to determine whether DLT has been identified in a subject who is confirmed to have received PB2452. If the SRC determines an AE is related to administration of ticagrelor or another confirmed cause, the AE will not be considered a DLT. Definitions of DLT are:

- Any AE assessed as \geq Grade 2 based on the CTCAE v5 grading scale and occurred in a subject confirmed to have received PB2452
- Any \geq Grade 2 laboratory abnormality (outside the clinical laboratory normal reference range) that occurs in a subject confirmed to have received PB2452
 - Note: For a Grade 2 electrolyte abnormality that spontaneously resolves to \leq Grade 1 without intervention within 24 hours, the SRC may decide to exempt the laboratory abnormality from being considered a DLT
- Any TEAE that leads to study withdrawal of a subject confirmed to have received PB2452

The SRC will provide an external spreadsheet which contains all DLT events and this external spreadsheet will be used in the summaries and listings.

8.1.5. Infusion Site Assessments

The infusion site will be examined by the investigator or designee concerning pain, tenderness, erythema/redness, and induration/swelling within 15 minutes before the initiation of the study drug infusion at Hour 0, and at 1, 3, 24, and 48 hours after initiation of the study drug infusion and on Day 7. Infusion site reactions will be assessed according to the CTCAE v5 grading scale and will be recorded as AEs and included in the AE listings.

8.1.6. Serious Adverse Events

An AE or suspected adverse reaction is considered as a serious AE (SAE)/suspected unexpected serious adverse reaction if, in the view of either the investigator or Sponsor, it results in any of the following outcomes

- Death
- Life-threatening AE
- Inpatient hospitalization or prolongation of existing hospitalization

- Persistent or significant incapacity or substantial disruption of the ability to conduct normal life functions
- Congenital anomaly or birth defect

All SAEs including deaths will be presented in a data listing, by Part.

8.1.7. Adverse Events Leading to Early Discontinuation

All AEs that lead to early discontinuation will be presented in a listing, by Part.

8.2. Clinical Laboratory Evaluations

Clinical laboratory tests will be performed by PPD Central Laboratory. Repeat clinical laboratory tests may be performed at the discretion of the investigator, if necessary, to evaluate inclusion and exclusion criteria or clinical laboratory abnormalities. The clinical laboratory performing the tests will provide the reference ranges for all clinical laboratory parameters.

The following clinical laboratory assessments will be performed:

Hematology	Complete blood count with differential hematocrit hemoglobin mean corpuscular hemoglobin mean corpuscular hemoglobin concentration mean corpuscular volume mean platelet volume platelet count erythrocyte (red blood cell [RBC]) count total and differential leukocyte (white blood cell [WBC]) count
------------	---

Other analyses	urine drug screen (Screening and Check-in only): amphetamines barbiturates benzodiazepines cannabinoids cocaine cotinine methylenedioxymethamphetamine opiates phencyclidine propoxyphene tetrahydrocannabinol urine alcohol (Screening and Check-in only) female subjects: follicle-stimulating hormone (Screening only) serum pregnancy test (human chorionic gonadotropin [Screening, Check-in, and Day 28 (± 2 days) only])
----------------	--

Hematology, clinical chemistry, coagulation, and urinalysis laboratory tests will be performed on Screening, at Check-in Days -3, on Days -1, 2, 7, and 28 (± 2).

Urine drug screen and urine alcohol screen tests will be performed on screening and at Check-in Day -3.

Serum pregnancy test will be performed on Screening, at Check-in Day -3, and on Day 28 (± 2).

Serology tests and stool occult blood will be only performed on Screening.

Abnormal clinical laboratory values will be flagged as either high or low (or normal or abnormal) based on the reference ranges for each laboratory parameter. The investigator will determine whether any of the abnormally high or low results are clinically significant (CS) or not CS (NCS).

The hematology and coagulation, clinical chemistry, and urinalysis test results will be presented in the data listings sorted by treatment group, subject, laboratory test, and sample collection date/time. Values that are outside of the normal range as well as the clinically significance information will be flagged in the listings. Actual results and change from baseline will be summarized for the safety population. Shift tables will be generated for the safety population.

All other laboratory tests will be presented in a data listing sorted treatment group, subject, laboratory test category, laboratory test, and sample collection date/time.

All laboratory tables and listings will be provided by Part.

